This is a prospective investigator initiated single-center open-label, non-placebo controlled pilot study. All patients meeting the inclusion criteria would be screened for eligibility and after informed consent, randomization would be performed to either the Cilostazol treatment (drug group) or the non-Cilostazol treatment (control group) groups, stratified for endovascular or open interventions, using a closed envelope randomization technique. Eligible patients would be consented prior to surgery or within 48 hours of index procedure. Patients on Cilostazol prior to surgery would still be eligible and medication discontinued if randomized to control group. Cilostazol will be provided to patients randomized to the treatment arm free of charge for three months. . If you are randomized to the treatment arm (receiving Cilostazol) we will provide you with Cilostazol 100 mg, twice a day, free of charge for a period of three months. Patients who have renal impairment (problems with their kidneys) will be given 50 mg, twice a day instead of 100 mg, twice a day. Cilostazol has a half- life of 13 hours, therefore a washout period will not be necessary. Concurrent medication use based on comorbidities including diabetic, anti-hypertensive medications, lipid lowering agents would be prescribed based on standard practice and not dependent on study group or enrollment in the study. Also concurrent use of single or dual antiplatelet therapy (aspirin with or without ADP receptor blocker or similar medication) would be used at discretion of treating physician. Patients who need to be on anticoagulation, with warfarin or other oral anticoagulants, for high risk revascularization or other comorbidities, would have single antiplatelet agent (as above) only for secondary prevention of thrombotic events. Cilostazol use in either group would not lead to a change in their antiplatelet/anticoagulation regimen.

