Pre-operative demographic, medication use and co-morbidity data and operative data would be retrieved from EMR. Patient follow up would be based on our current standard protocol which includes duplex of the graft or intervened artery at 4-6 weeks and 3-6 months. Cilostazol will be provided to patients free of charge for three months. Restenosis is defined as stenosis>50% based on our current vascular laboratory criteria or based on arteriogram imaging if performed at discretion of treating physician. Clinical examination and medication use and other secondary and adverse outcomes would be evaluated and QOL questionnaires administered at above time points. Quality-of-life (QOL) questionnaires (EQ-5D and EACH Qc) will be administered at enrollment and each follow up visit.

Purpose

The primary purpose of this pilot study is to collect QOL data on patients undergoing peripheral revascularization in order to determine the sample size required for adequate powered trial of Cilostazol versus usual care without Cilostazol and its effect on QOL. Thirty patients, fifteen in each arm, will be recruited into the pilot study in order to obtain sufficient data needed to estimate the variance and within-subject correlation of the outcome measures.

Benefits/Risks

Benefits include: possible improvement in quality of life for patients suffering from claudication after revascularization, improvement in graft patency and decreased restenosis and potential amputation. Risks include possible allergic reaction to the drug.

Inclusion

1. Patients should be older than 35 years of age
2. Patients treated for atherosclerotic PAD
3. Able to provide informed consent
4. Lower extremity open or endovascular revascularization, including bypass (autogenous or prosthetic), angioplasty and/or stenting, with or without concomitant aorto-iliac intervention.

Exclusion

1. Known congestive heart failure Class III/IV, systolic, acute or chronic
2. Allergic reaction to phosphodiesterase inhibitors
3. Intracranial bleeding within 3 months or active bleeding peptic ulcer disease
4. Traumatic vascular injuries requiring revascularization

5. Pregnant or breast feeding women, or plan to get pregnant over the study period (for five years after enrollment)
6. Planned ipsilateral major amputation within 30 days of index procedure
7. Moderate to severe hepatic impairment

Analysis

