Data will be collected and stored on a password protected secure server which only study team members can access. QOL instruments (EQ-5D and EACH Qc) will be scored from the baseline, 4-6 week and 3 month visits. Cross-sectional and change scores will be calculated to estimate effect size and variance of QOL outcomes measures. These data will be used to assess potential efficacy and to project sample size requirements for a future trial. Treatment arm differences in early (4-6 week) and late (3 month) month changes in QOL scores will be tested using two-group t-tests.

Follow-up graft patency will be assessed as a secondary outcome and will be measured early (within 14 day of intervention) and late (six weeks and three months) using duplex ultrasound.

Treatment arm differences time to patency failure will be compared using Kaplan-Meier survival curves and log-rank tests. Information on the following tertiary outcomes will also be ascertained at six weeks and three months follow-up: (1) amputation, (2) death due to any cause, (3) clinical symptoms of claudication or rest pain (critical limb ischemia), and (4) stroke. Statistical comparison for differences between groups will not be performed for tertiary outcomes due to small sample size and power.

Confidentiality and Privacy

Confidentiality will be protected by collecting only information needed to assess study outcomes, minimizing to the fullest extent possible the collection of any information that could directly identify subjects, and maintaining all study information in a secure manner. To help ensure subject privacy and confidentiality, only a unique study identifier will appear on the data collection form. Any collected patient identifying information corresponding to the unique study identifier will be maintained on a separate master log. The master log will be kept secure, with access limited to designated study personnel. Following data collection subject identifying information will be destroyed at the earliest opportunity, consistent with data validation and study design, producing an anonymous analytical data set. Data access will be limited to study staff. Data and records will be kept locked and secured, with any computer data password protected. No reference to any individual participant will appear in reports, presentations, or publications that may arise from the study.

Data and Safety Monitoring

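### Admitting prior cilostazol users makes the QOL change scores a mix of starting, continuing, never using and withdrawing the drug, and no planned analysis separates them

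*Combined protocol and SAP*

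**What the plan says.** The relevant statements are spread over the Methods, Purpose and Analysis sections of the combined protocol and SAP.

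- Eligibility and handling (Methods): "Patients on Cilostazol prior to surgery would still be eligible and medication discontinued if randomized to control group". By implication, prior users randomized to the drug arm stay on it.
- Washout (Methods): "Cilostazol has a half- life of 13 hours, therefore a washout period will not be necessary".
- Timing of entry and baseline (Methods): "Eligible patients would be consented prior to surgery or within 48 hours of index procedure"; "Quality-of-life (QOL) questionnaires (EQ-5D and EACH Qc) will be administered at enrollment and each follow up visit".
- Randomization (Methods): "stratified for endovascular or open interventions, using a closed envelope randomization technique". Prior cilostazol use is not a stratum.
- Data available (Methods): "Pre-operative demographic, medication use and co-morbidity data and operative data would be retrieved from EMR".
- Size (Purpose): "Thirty patients, fifteen in each arm, will be recruited into the pilot study". The justification is estimation of the variance and within-subject correlation of the outcome measures.
- Analysis: "Cross-sectional and change scores will be calculated to estimate effect size and variance of QOL outcomes measures". These estimates are to inform the size of a future trial. Arm differences in early and late QOL change are tested by two-group t-tests with no covariates. Prior cilostazol use enters no analysis.

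**The concern.** The half-life argument deals with drug carried over into follow-up. It does not deal with a baseline QOL score recorded while the patient is taking the drug. For such a patient, change from baseline does not measure what it measures in someone who has never taken cilostazol. Leaving aside the effect of the procedure, which both arms share, there are four patterns:

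| | Drug arm | Control arm |
|---|---|---|
| Not on cilostazol at enrollment | starts: gain | never on: no drug-related change |
| On cilostazol at enrollment | continues: no drug-related change | withdraws: loss |

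The pilot's product is a set of planning inputs: effect size, variance and within-subject correlation. All three would come from this mixture, without any record of how much each pattern contributed. If the future trial has a different share of prior users, or none, the inputs would not carry over to it.

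**Working it through.** **The plan's own figure.** 2 x 15 = 30 is consistent, but no effect size, SD, correlation or precision target is stated, so 30 cannot be derived. The precision it implies is: 95% interval for a pooled SD (28 df), 0.79 to 1.35 times the estimate; for a correlation of 0.5 with n = 30, 0.17 to 0.73.

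**Is the baseline on drug?** This is an inference from three statements: no washout, QOL at enrollment, and discontinuation only after randomization to control. Consent may come up to 48 hours after the procedure. If a patient's drug had been paused for the whole of that time, 0.5^(48/13) = 0.08 would remain, but the documents describe no such pause. Hence generally, not always, on drug.

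**Model.** Let p be the share of prior users, g the gain on starting, l the loss on stopping and rho the off-drug correlation. The cross-sectional SD is 1. Effects are taken as additive, with the same underlying variability in prior users and others. The documents give none of p, g, l or rho; I assume p = 0.2 to 0.4, g = 0.5 and rho = 0.5 to 0.7.

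**Effect.** Expected arm difference in change = (1 - p)g + p l. This equals g only if l = g.

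**Variance.** Change-score variance = 2(1 - rho) + p(1 - p)g² in the drug arm, and the same with l² in control. With l = g the inflation is p(1 - p)g² / [2(1 - rho)]:
- p = 0.2, rho = 0.5: 0.16 x 0.25 / 1.0 = 4%
- p = 0.4, rho = 0.7: 0.24 x 0.25 / 0.6 = 10%

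**Correlation.** With l = g it becomes rho / sqrt(1 + p(1 - p)g²). From 0.500 it falls to 0.490 (p = 0.2) or 0.486 (p = 0.4). With l = 1.5g and p = 0.3 it falls to 0.473 in control but rises slightly, to 0.507, in the drug arm.

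**Future sample size under asymmetry**, with the SD held fixed. The multiplier is [g / ((1 - p)g + p l)]²:
- l = 0.5g: 1/0.9² = 1.23 to 1/0.8² = 1.56, so +23% to +56%
- l = 1.5g: 1/1.1² = 0.83 to 1/1.2² = 0.69, so -17% to -31%

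Letting the SD change as well (g = 0.5, rho = 0.5):
- l = 0.5g: 1.025/0.81 = 1.27 to 1.0375/0.64 = 1.62
- l = 1.5g: 1.065/1.21 = 0.88 to 1.0975/1.44 = 0.76

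As a worked case at p = 0.3 (two-sided 0.05, 80% power), n per arm is 63 with no prior users, 67 if l = g, 90 if l = 0.5g and 52 if l = 1.5g. A simulation at p = 0.3 agreed with the closed forms for effect, SD and correlation.

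**Chance imbalance.** SD of the arm difference in prior-user share = sqrt(2p(1 - p)/15) = 0.146 (p = 0.2), 0.167 (0.3), 0.179 (0.4). A difference of at least 20 points (3 patients) has probability 0.25, 0.32 and 0.35. Under symmetry the estimated effect shifts by g times the imbalance, so the SD of that shift is 0.07 to 0.09. The standard error of the difference at rho = 0.5 is about sqrt(2/15) = 0.37. The inflated change-score variance already contains this shift, so it should not be counted twice.

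**What adjustment does** (g = l = 0.5, rho = 0.6). Change-score variance is 0.80 + 0.04 = 0.84 to 0.80 + 0.06 = 0.86. ANCOVA on baseline QOL alone gives 0.65 to 0.66; adding prior use gives 1 - 0.36 = 0.64. Under half-withdrawal at p = 0.4 the arm difference is 0.6 x 0.5 + 0.4 x 0.25 = 0.40, and simulation gave 0.40 with and without the covariate.

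**The case against.** The strongest reply is that randomization protects the comparison. Both arms have the same expected share of on-drug baselines, so a reader who infers that the arm comparison is simply biased goes beyond the documents. That stands: with symmetric starting and stopping effects the contrast is unbiased on average. The documents do not say whether the effects are symmetric. The trial is open-label and the outcome self-reported, so knowingly losing a current drug need not mirror never starting it. The direction of any departure is equally open, so quoting only the case that inflates the sample size would be one-sided.

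A reader might also infer that the future trial will enroll new users only, which would make the naive estimates the right ones. The Purpose section says only that it would compare cilostazol with usual care without it. This pilot deliberately admits prior users; if the future trial does the same in similar proportion, the mixed estimates suit it.

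The size is also open to challenge, and rightly. With symmetric effects at 0.5 SD, the shifts in SD and correlation lie well inside the sampling error at 30 patients. A figure of 43% for a 20-point imbalance can be obtained by fixing exactly nine prior users, but that depends on the odd count: with 6, 8, 10 or 12 it is 17-26%.

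Finally, cross-sectional scores are planned as well. At follow-up they do not use the baseline, so an on-drug baseline cannot inflate their SD. They would not cure asymmetric withdrawal, and the planned tests are on change scores.

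**Conclusion.** The point holds as a cheap improvement to the analysis, not as a flaw that invalidates the comparison. The change scores pool four drug histories. The pooled effect is a pure starting effect only if stopping loses what starting gains. Under the additive model, the change-score SD is raised whenever the drug affects QOL; the within-subject correlation is lowered in both arms under symmetry and lowered on average over the arms in the asymmetric cases run.

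The size is conditional on a prior-user share and QOL effect that the documents do not give. Under symmetry it is minor. Under asymmetry it could move the projected sample size materially in either direction. Confidence is high that the mixture exists if prior users enroll, and low on how large its effect is.

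**What to change.** Change the analysis wording only:

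1. Derive a yes/no variable for cilostazol use at enrollment from the pre-operative medication data, and tabulate it by arm.
2. Compare arms at 4-6 weeks and 3 months by ANCOVA on follow-up QOL, with baseline QOL and prior use as covariates. Most of the precision gain comes from baseline QOL.
3. Because a prior-use covariate does not correct asymmetric withdrawal, also report the arm difference, SD and within-subject correlation in cilostazol-naive patients, beside the all-patient estimates.
4. State that the future trial will be sized from the set that matches its eligibility: naive estimates if it excludes prior users, mixed estimates if it admits them.

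The cost is one degree of freedom per covariate (28 to 26 with both) and wider naive-only intervals. With 20-40% prior users, 18 to 24 patients remain. At 18 the 95% interval for the SD is about 0.74 to 1.52 times the estimate, against 0.79 to 1.35 for all 30. Eligibility, treatment and data collection are unchanged.

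### The pilot's own QOL effect estimate is left available as the target difference for the future trial, although 15 patients per arm estimate it only to about ±0.75 SD

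*Combined protocol and SAP*

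**What the plan says.** The Purpose section gives the pilot's aim as collecting QOL data to "determine the sample size required for adequate powered trial of Cilostazol versus usual care without Cilostazol and its effect on QOL". It sets the size: "Thirty patients, fifteen in each arm, will be recruited into the pilot study". The only reason given is to obtain "sufficient data needed to estimate the variance and within-subject correlation of the outcome measures". Effect size is not mentioned there.

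The Analysis section goes further: "Cross-sectional and change scores will be calculated to estimate effect size and variance of QOL outcomes measures". The next sentence gives two uses: "These data will be used to assess potential efficacy and to project sample size requirements for a future trial". The arm comparison follows: "Treatment arm differences in early (4-6 week) and late (3 month) month changes in QOL scores will be tested using two-group t-tests".

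The one caution about sample size in that section concerns other endpoints: "Statistical comparison for differences between groups will not be performed for tertiary outcomes due to small sample size and power". The document states no important QOL difference, no precision requirement for the effect estimate, and no limit on how that estimate may be used.

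**The concern.** A sample-size projection for a comparison of means needs an SD and a target difference. The Purpose section covers the SD. For the target difference, the only candidate the plan names is the pilot's own estimate, which the Analysis section places beside the variance among the results used for the projection.

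Required n is proportional to 1/d², so error in d is amplified. A pilot that is favourable by chance yields a trial far too small. One that is unfavourable by chance yields a trial several times too large, or no trial at all. What is at stake is the pilot's main product. This study's participants and its own estimates are not affected.

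**Working it through.** **Inputs.** From the Purpose section: 30 patients, 15 per arm. From the Analysis section: two-group t-tests, so 28 degrees of freedom if all 30 are evaluable. Not stated, hence assumed: two-sided 0.05, 80% power for the future trial, equal SDs set to 1, and true effects d of 0.2, 0.3, 0.5 and 0.8 SD. The plan's figure of 30 cannot be reproduced, because no numerical input is given for it.

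**Precision of the effect.** SE = √(2/15) = 0.365 SD. Half-width = t(0.975, 28) × SE = 2.048 × 0.365 = 0.748 SD. With 12 evaluable per arm (assumed 20% loss), t(0.975, 22) × √(2/12) = 0.847 SD. By the exact noncentral-t interval, an observed d of 0.5 has a 95% CI of −0.23 to 1.22.

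**Precision of the variance, for contrast.** With 28 df the 95% CI runs from 0.63 to 1.83 times the observed variance, or 0.79 to 1.35 times the observed SD.

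**Using the observed effect as the target.** Projected n per arm = 2(1.96 + 0.8416)²/d̂² = 15.70/d̂², rounded up. True power is approximately Φ(d√(n/2) − 1.96). Ignoring rounding, this falls below 50% when d̂ exceeds d × 2.8016/1.96 = 1.43d. At d = 0.5 that means any pilot estimate above about 0.71. Results from 1,000,000 simulated pilots per true d, with the trial run on any positive estimate:

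| True d (SD) | 0.2 | 0.3 | 0.5 | 0.8 |
|---|---|---|---|---|
| n per arm needed | 393 | 175 | 63 | 25 |
| Pilot estimate ≤ 0, no projection | 29% | 21% | 8.5% | 1.4% |
| Mean true power of trials run | 49% | 59% | 69% | 75% |
| True power < 50%, of trials run | 58% | 46% | 31% | 20% |
| True power < 50%, of all pilots | 41% | 37% | 28% | 20% |
| True power < 50%, of trials run, if none above 500 per arm is run | 78% | 58% | 35% | 21% |
| True power < 50%, of trials run, 12 evaluable per pilot arm | 61% | 50% | 34% | 23% |

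The all-pilots row is the share of trials run times the chance of a positive estimate, e.g. at d = 0.5, 0.310 × (1 − 0.085) = 0.284. With the assumed limit of 500 per arm it is the same: 0.349 × 0.813 = 0.284. The limit removes only large trials from the denominator, so the undersized trials do not arise from accepting very small positive estimates.

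At d = 0.5 the 10th to 90th percentile of projected n, given a positive estimate, is 15 to about 590 per arm.

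**A pilot that just reaches p = 0.05.** d̂ = 0.748 gives 15.70/0.748² = 28.1, so 29 per arm. True power is then 12, 21, 48 and 86% at the four true effects.

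**Fixed target, SD from the pilot.** Now n = 15.70 s²/target², and only s² is random. Its 10th and 90th percentiles are 18.94/28 = 0.68 and 37.92/28 = 1.35 times the true variance, so n varies by those factors. With target and truth both 0.5 SD, n runs from 43 to 86, mean power is 78%, and about 1% of trials fall below 50% power.

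**The case against.** The strongest reply is that the plan never says the observed difference will be the target. The Analysis section names two estimates and two uses, and can be read as pairing effect size with potential efficacy and variance with the projection. The Purpose section supports that reading. A target difference can also be left to the future trial's protocol. The Background says QOL with cilostazol after revascularisation has not been studied, so describing an effect estimate is a reasonable pilot output. This stands to the extent that the use is permitted, not mandated, and every power figure above depends on it. It does not remove the problem, because the text assigns both estimates to both uses without distinction and names no other source for the most influential input.

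A second reply is that a fixed target may be wrong, and this also stands. With target 0.5 and true d 0.3, mean power is 39% and 90% of trials fall below 50% power, against 59% and 46% when the observed effect is used. The case for a fixed target is that power is controlled at a difference judged worth detecting, not that power is better against an unknown truth.

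Two smaller points are fair. The simulation turns one estimate mechanically into n, whereas the plan has two instruments, two follow-up visits and two kinds of score. The contrast with the tertiary outcomes is only suggestive, since that caution concerns testing. If effect size meant change within one arm, the half-width would be about 0.55 SD (2.145/√15), but the stated efficacy use and the between-arm tests make the arm difference the better reading.

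**Conclusion.** The concern holds. The Analysis section lists the effect size among the results that will size the next trial. The Purpose section justifies 15 per arm only for variance and within-subject correlation. At that size the arm difference is known to about ±0.75 SD, or ±0.85 SD with 12 evaluable per arm. If the estimate is used as the target, 20 to 58% of the resulting trials have true power below 50% over true effects of 0.8 down to 0.2 SD. This assumes two-sided 0.05, 80% power, all 30 evaluable and a trial run on any positive estimate. The half-width needs only the evaluable numbers, the 95% level and equal SDs. The consequence is conditional and falls on the future trial, but it affects this pilot's primary purpose and should be corrected before the data are analysed. Confidence is medium, because the wording allows the narrower reading.

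**What to change.** Replace the sentence on use of the data in the Analysis section with wording such as:

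> The future trial will be sized on a clinically important difference of [x] in [named QOL score] at [visit], fixed and justified before the pilot data are analysed. The pilot will supply only the SD and the within-subject correlation of that score, each with a 95% CI. The pilot arm difference will be reported with its 95% CI and will not be used as the target difference.

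This brings the Analysis section into line with the reason the Purpose section gives for 30 patients. It needs no extra patients or data. The cost is that the team must choose and defend a difference, and the projected n may be larger or smaller than the observed effect would have suggested. If the true effect is below the target, power is lower, as in the example of target 0.5 and true 0.3. If it is above, the trial is larger than that effect needs: with target 0.3 and true d 0.5, mean power is 99%.

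### Eight pilot QOL effect estimates and four t-tests feed the efficacy reading and the future sample size with none designated, and no pilot effect size is precise enough at 15 per arm to size a trial on

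*Combined protocol and SAP*

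**What the plan says.** The Purpose section makes the later trial's sample size the pilot's main product: "The primary purpose of this pilot study is to collect QOL data on patients undergoing peripheral revascularization in order to determine the sample size required". It sets recruitment as "Thirty patients, fifteen in each arm, will be recruited into the pilot study", and the only reason it gives for that number is that variance and within-subject correlation can then be estimated.

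The Analysis section goes further. "QOL instruments (EQ-5D and EACH Qc) will be scored from the baseline, 4-6 week and 3 month visits". Then: "Cross-sectional and change scores will be calculated to estimate effect size and variance of QOL outcomes measures". The next sentence gives the use: "These data will be used to assess potential efficacy and to project sample size requirements for a future trial". Then: "Treatment arm differences in early (4-6 week) and late (3 month) month changes in QOL scores will be tested using two-group t-tests".

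No section ranks the two instruments, the two follow-up visits or the two score types. The Methods section names both instruments side by side. The plan states no significance level and no multiplicity rule, and does not say which estimate enters the sample-size calculation. For tertiary outcomes, the Analysis section declines between-arm tests because the sample is small.

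**The concern.** A pilot need not control familywise error, and that is not the point here. This pilot's one deliverable is a set of inputs to a sample-size calculation, and the plan does not say which of several candidates they are. The SD and the within-subject correlation also differ by instrument and visit, so the gap remains even if effect sizes are set aside.

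The Analysis section also adds effect size to what will be estimated and links the results to efficacy and sample size, whereas the Purpose section relies on variance and correlation alone. If a pilot effect size is used, two problems follow. A choice made after the results are seen tends to favour a chance-high estimate. Even without such a choice, an effect estimated from 15 per arm is too noisy to size on. Either can leave the later trial much too small.

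**Working it through.** **Inputs from the protocol.** 2 instruments, 2 follow-up visits and 2 score types (Analysis); 30 patients, 15 per arm (Purpose).

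**Assumptions, because the protocol gives no values.** Two-sided 5% level; 80% power for the later trial; effects in SD units (d); correlations between outcomes of 0 to 0.7; no dropout. True d = 0.3 is illustrative.

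**The plan's own figure.** The 30 cannot be reproduced, since no precision target is given. What it delivers is 28 degrees of freedom for a pooled SD, with 95% limits of 0.794 to 1.352 times the estimate. Sample size varies with the SD squared, so the projected N has limits of 0.794² = 0.63 to 1.352² = 1.83 times its value.

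**Counts.** Effect estimates: 2 × 2 × 2 = 8. The t-tests cover changes only: 2 × 2 = 4.

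**Any nominally significant test under no effect.** If independent, 1 − 0.95⁴ = 18.5% in either direction, and 1 − 0.975⁴ = 9.6% favouring cilostazol. Correlation lowers both. Simulation with four equally correlated outcomes and 15 per arm gives:

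| Correlation | Any p<0.05, no effect | Mean largest of 4, no effect | Mean largest of 4, true d = 0.3 |
|---|---|---|---|
| 0 | 18.5% (exact) | 0.39 | 0.70 |
| 0.3 | 18% | 0.33 | 0.64 |
| 0.5 | 16% | 0.28 | 0.59 |
| 0.7 | 13% | 0.21 | 0.53 |

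At correlation 0.7 the chance of a false result favouring cilostazol is about 7%. One test gives 2.5% in that direction.

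A model closer to the design (baseline and two visits, two instruments, between-instrument correlation 0.3 to 0.7, within-subject correlation 0.5 to 0.7) gives 15% to 17% for any p<0.05.

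**Worst-case effect on the later trial.** N per arm = 2(1.96 + 0.84)²/d².

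- d = 0.30: 2 × 7.85/0.09 = 174.4, or 176 with the t correction.
- d = 0.57: 2 × 7.85/0.325 = 48.3, or 50 with the t correction.

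The value 0.57 lies in the 0.53 to 0.70 range above, toward its lower end. A trial of 50 per arm has about 32% power at d = 0.3. If the largest of all eight estimates were taken (structured model, within-subject correlation 0.5, true d = 0.3 on both score types), the median is 0.71 to 0.76. That implies 28 to 32 per arm.

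**One prespecified estimate.** SE = √(2/15) = 0.365. The 95% interval is ±2.048 × 0.365 = ±0.75. With true d = 0.3:

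- P(estimate > 0.57): (0.57 − 0.30)/0.365 = 0.74, giving 23%, or 24% with the t distribution.
- P(estimate ≤ 0): −0.30/0.365 = −0.82, giving 20.6%.

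**Why adjust for baseline.** With equal variances and within-subject correlation ρ, the variance is proportional to 2(1 − ρ) for change and 1 − ρ² after adjustment. At ρ = 0.5 these are 1.00 and 0.75; at ρ = 0.7 they are 0.60 and 0.51. The adjusted analysis is never worse, and it uses the two quantities the Purpose section sets out to estimate.

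**The case against.** The strongest reply has four parts.

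*The protocol never says the largest estimate will be used.* This is correct. A reader might infer that the sponsor plans to pick the best result. The text supports only that nothing rules it out, so the 50-versus-176 comparison is a worst case and not a forecast.

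*The Purpose section sizes the pilot on variance and correlation, which selection hardly disturbs.* This is also correct. In simulation at true d = 0.3, the SD of the outcome with the largest effect averages 0.966 to 0.972, against 0.991 without selection. That is 2% to 2.5% in SD, or about 4% to 5% in N. But the Analysis section does estimate effect size and does refer to efficacy, so the plan cannot be read as confined to variance.

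*Naming a primary measure does not cure the sizing problem.* This stands. A single prespecified d still exceeds 0.57 in about 24% of pilots at true d = 0.3. What removes the danger is not sizing on pilot d at all.

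*Comparing several candidate measures is a proper aim for a pilot.* This stands too. It is met by describing every measure's SD and correlation, and does not require unranked tests.

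**Conclusion.** The concern holds in limited form. Up to eight effect estimates and four tests are linked to an efficacy reading and to the pilot's main deliverable, with none designated, and the plan leaves open sizing on an effect estimate whose 95% interval is about ±0.75 SD.

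The 13% to 18.5% figure might be read as the chance of a false efficacy signal. It is not: it counts results in both directions. The chance of a false signal favouring cilostazol is about 7% to 10%, against 2.5% for one test, so it is roughly three to four times as likely. The worst-case sizing error is about 50 per arm against about 176. It depends on the largest of four estimates being chosen, which the protocol does not state.

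All these magnitudes rest on assumed correlations, a 5% two-sided level, 80% power and no dropout. Patient safety is not affected. The pilot's stated purpose is, so the point should be settled before the arms are compared.

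**What to change.** Before any arm comparison is seen:

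1. Name one instrument and one visit as the primary QOL measure, for example the 3-month EQ-5D index, or EACH Qc if the sponsor prefers. Analyse it with adjustment for its baseline score in place of the unadjusted change-score t-test, and use only that contrast for any statement on potential efficacy.
2. Project the later trial's sample size from that measure's SD and within-subject correlation, with confidence limits, and a target difference set independently of the pilot's observed effect. Do not size on the pilot effect.
3. Report all other QOL contrasts, and the SDs and correlations of the other measures, descriptively with 95% confidence intervals and no p-values.

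This takes a few sentences in the Analysis section and no extra patients, visits or data. The price is that the other QOL contrasts become supportive only, and that the target difference has to be justified from outside the pilot.
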